9. **CCI**

10. Patients at 1 clinical investigative site will undergo **CCI** during Screening and at the Week 24 Visit and Week 48 Visit (proptosis non-responders who elect to receive open-label TEPEZZA). The Week 24 **CCI** will not need to be performed on the same day as other Week 24 assessments as long as it is performed within the visit window and prior to the Week 24 infusion (proptosis non-responders who elect to receive open-label TEPEZZA). The Week 48 **CCI** will not need to be performed on the same day as other Week 48 assessments as long as it is performed within the visit window.

11. Clinical Activity Score must be <1 in both eyes at the Screening and Baseline Visits.

12. For women of childbearing potential (including those with an onset of menopause < 2 years prior to Screening, non-therapy-induced amenorrhea for < 12 months prior to Screening, or not surgically sterile [absence of ovaries and/or uterus]), a serum pregnancy test will be performed at Screening and urine pregnancy tests will be performed prior to dosing at all other visits, as applicable, and at the End-of-Treatment Visit.

13. Patients who have decreased best-corrected visual acuity due to optic neuropathy (defined by a decrease in vision of 2 lines on the Snellen chart, new visual field defect, or color defect secondary to optic nerve involvement within the last 6 months) are not eligible for randomization.

14. Vital signs (blood pressure, heart rate, respiratory rate, temperature) will be measured at all clinic visits. Vital signs will be measured pre- and post-infusion on Day 1 and Week 3 (all patients), pre- and post-infusion at Week 24 and Week 27 (proptosis non-responders who elect to receive open-label TEPEZZA) and pre-infusion on all other infusion days. Additional vital signs will be monitored if infusion-associated AEs occur (see Section 9.5.3.4 for details).

15. Patients must be euthyroid, with the Baseline disease under control or have mild hypo- or hyperthyroidism (defined as FT4 and FT3 levels < 50% above or below the normal limits). Every effort should be made to correct the mild hypo- or hyperthyroidism promptly and to maintain the euthyroid state for the full duration of the trial.

16. HbA1c must be < 8.0% to be eligible for the trial. If the HbA1c is elevated and considered clinically significant at any time point after Screening, it will be repeated approximately every 90 days until it returns to normal or Baseline value.

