### **9.4 Treatments**

#### **9.4.1 Treatments Administered**

The first 2 infusions of the double-masked and open-label Treatment Periods will be administered over approximately 90 minutes (but not less than 80 minutes). All subsequent infusions will be administered over approximately 60 minutes (but not less than 50 minutes). For the first 3 infusions, patients will be monitored for any AEs during the infusion and for 60 minutes after completion of the infusion. For subsequent infusions (if no previous infusion reactions), patients will be monitored during and for 30 minutes after completion of the infusion. At any scheduled infusion, the infusion rate may be reduced or the dose interrupted or held based on tolerability (see [Section 9.4.6.3.2](#) for details).

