#### **9.4.6.3.2 Dose Modifications, Interruptions and Delays**

All dosing instructions are applicable for TEPEZZA and placebo administration.

Patients will be evaluated for safety throughout the trial. For the first 3 infusions, patients will be monitored for any AEs during the infusion and for 60 minutes after completion of the infusion for immediate infusion-associated events (e.g., transient increase in blood pressure, feeling hot, tachycardia, dyspnea, headache and muscular pain) and delayed infusion-associated events (e.g., rash). For subsequent infusions (if no previous infusion reactions), patients will be monitored during and for at least 30 minutes after completion of the infusion.

If immediate infusion-associated events are noted, the infusion rate may be slowed or interrupted and symptomatic treatment (e.g., antipyretics, antihistamines, beta-agonists, glucocorticoids, oxygen, IV fluid) may be administered, as necessary. Vital signs (temperature, blood pressure, pulse and respiratory rate) will be monitored every 5 minutes until stable and then every 15 minutes for 2 additional determinations. The infusion may be restarted upon complete resolution of symptoms; however, TEPEZZA dosing will be permanently discontinued if the event is an anaphylactic reaction.

If delayed infusion-associated events are noted, patients may continue dosing at the Investigator's discretion; however, if a rash worsens following repeated dosing or other signs of serum sickness (e.g., delayed fever, myalgias, arthralgias) are present, TEPEZZA dosing will be permanently discontinued. If an infusion-associated event is experienced after patients are discharged from the site, the Investigator is to be contacted as soon as possible.

Following the appearance of either immediate or delayed infusion-associated events, patients who receive subsequent doses may be pre-treated with diphenhydramine (1 to 1.25 mg/kg IV; maximum of 50 mg), ranitidine (50 mg IV), famotidine (0.5 mg/kg IV), dexamethasone (0.4 mg/kg IV; maximum of 20 mg) and/or acetaminophen (500 mg). All subsequent infusions will be administered over approximately 90 minutes (but not less than 80 minutes) with vital signs monitored every 15 minutes from the start of the infusion through 60 minutes after completion of the infusion.

In general, the decision to continue dosing should take into consideration the potential benefit and risk to a patient.

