#### **Risk of Hypersensitivity (Infusion-related events)**

- Administration of mAbs may cause infusion-related symptoms, such as fever, chills, hypotension, shortness of breath, skin rash and headache. Such reactions typically occur

during or shortly after the infusion of mAbs and are usually associated with the first infusion. Their incidence and severity typically decrease with subsequent infusions. Severe infusion-related reactions might be clinically indistinguishable from anaphylactic reactions.

- Infusion-related events observed with teprotumumab to date have not been anaphylactic in nature. However, because of the protein nature of teprotumumab and the potential for infusion-related reactions and hypersensitivity reactions, teprotumumab should be administered in a setting with emergency equipment and staff who are trained to monitor medical situations and respond to emergencies. For the first 3 infusions, patients should be monitored for any events during infusion and for 60 minutes after completion of infusion. For subsequent infusions (the fourth dose and beyond), patients who have not previously experienced an infusion reaction should be monitored during the infusion and for at least 30 minutes after the infusion.
- Patients who exhibit immediate hypersensitivity reactions or infusion-related reactions during an infusion of teprotumumab should have the infusion interrupted or the infusion rate slowed. Symptomatic treatment, e.g., antipyretics, antihistamines and/or corticosteroids, oxygen, beta agonists and IV fluids, should be administered to the patient. Following an immediate hypersensitivity reaction or infusion-associated reaction, vital signs (temperature, blood pressure, pulse and respiratory rate) will be monitored every 5 minutes until stable, and then every 15 minutes for 2 additional determinations. The infusion may be restarted upon complete resolution of symptoms except in the case of patients who experience an anaphylactic reaction of life-threatening intensity; these patients should be removed from the trial.

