- In general, the decision to keep a patient on trial treatment with teprotumumab should take into consideration potential risks and benefits to the patient. Prior to future infusions of teprotumumab, these patients may be premedicated with IV diphenhydramine 1 to 1.25 mg/kg (maximum 50 mg), IV ranitidine 50 mg, IV famotidine 0.5 mg/kg, IV dexamethasone 0.4 mg/kg (maximum 20 mg) and/or acetaminophen 500 mg. In addition, all future infusions should be administered over 90 minutes. Vital signs should be taken every 15 minutes during the infusion through 60 minutes after infusion completion.
- Patients who experience delayed-type hypersensitivity reactions (e.g., skin rash) may remain in the trial at the discretion of the Investigator and, prior to all future infusions of teprotumumab, may be premedicated with the above medications (diphenhydramine, ranitidine, famotidine, dexamethasone and acetaminophen). However, if a rash worsens

following repeated dosing or other signs of serum sickness (e.g., delayed fever, myalgias, arthralgias) are present, trial drug dosing will be permanently discontinued.

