#### 9.5.3.4 Vital Signs and Weight

Detailed timing of vital sign and weight measurements is described in Section 2.1.

Vital signs (blood pressure, heart rate, respiratory rate, temperature) will be measured at all clinic visits. Vital signs will be measured pre- and post-infusion on Day 1 and Week 3 (all patients), pre- and post-infusion at Week 24 and Week 27 (proptosis non-responders who elect to receive open-label TEPEZZA) and pre-infusion on all other infusion days. In addition, if immediate infusion-associated events are noted during the infusion, vital signs will be monitored every 5 minutes until stable and then every 15 minutes for 2 additional determinations. Also, vital signs will be monitored every 15 minutes from the start of the infusion through 60 minutes after infusion completion for any subsequent infusions after the previous occurrence of immediate or delayed infusion-associated events.

Blood pressure and pulse measurements will be obtained with the patient's arm unconstrained by clothing or other material and while the patient is sitting up. When possible, the same arm will be used for measurements at all trial visits.

Weight will be measured at Screening and Weeks 9 and 24 (or PW1) (all patients) and Weeks 33 and 48 (or PW2) (proptosis non-responders who elect to receive open-label TEPEZZA). The dose on Day 1 and Weeks 3, 6 and 9 of the double-masked Treatment Period will be based on the Screening weight; weight measured at Week 9 will be used in dose calculations at Weeks 12, 15, 18 and 21. The dose on Weeks 24, 27, 30 and 33 of the open-label Treatment Period will be

based on the Week 24 weight; weight measured at Week 33 will be used in dose calculations at Weeks 36, 39, 42 and 45.

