- Collect predose urine sample for a pregnancy test for females of childbearing potential; the pregnancy test must be negative for the patient to receive trial drug.
- Inquire about AEs and concomitant medication use.
- Measure predose weight (Week 9 only).
- Record vital signs prior to the infusion. Additional vital sign monitoring may be performed in the event of infusion-associated AEs (see [Section 9.5.3.4](#) for details).
- Obtain calculated trial drug dose, vial assignment (if applicable) and volume of trial drug to be administered from the EDC system.
- Administer trial drug and record date, volume and start/stop times of the infusion. Monitor the patient for any AEs during the infusion and for 30 minutes after the completion of the infusion.
- Enter visit data in the EDC system.

Patients will be discharged from the site after all procedures have been completed and instructed to return for a clinic visit in 3 weeks.

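### Visit checklists set a flat 30-minute post-infusion AE watch by calendar week, dropping the two conditions the dosing sections attach to it (minor safety wording)

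*Protocol*

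**What the plan says.** The protocol states the length of the post-infusion watch in two kinds of place.

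**Visit checklists.** Section 9.5.6.2.4 (Weeks 9, 15 and 21) says: "Monitor the patient for any AEs during the infusion and for 30 minutes after the completion of the infusion". Section 9.5.6.3.3 repeats this for Weeks 33, 39 and 45. Sections 9.5.6.2.3 and 9.5.6.3.2 give 30 minutes at Weeks 12 and 18 and at Weeks 36 and 42. None of these lines carries a condition. Each of the four checklists also says that extra vital signs may be taken for infusion-associated AEs, with a pointer to Section 9.5.3.4.

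**Dosing and safety sections.** Section 9.4.1 sets 60 minutes for the first three infusions and then says: "For subsequent infusions (if no previous infusion reactions), patients will be monitored during and for 30 minutes after completion of the infusion". The synopsis and Section 9.4.6.3.1 say the same. Section 9.4.6.3.2 keeps the condition and makes 30 minutes a minimum: "For subsequent infusions (if no previous infusion reactions), patients will be monitored during and for at least 30 minutes after completion of the infusion". Section 9.5.3.1.1.5 restricts the shorter watch, from the fourth dose on, in the same way: "patients who have not previously experienced an infusion reaction should be monitored during the infusion and for at least 30 minutes after the infusion".

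**After a reaction.** For patients who continue dosing, Section 9.4.6.3.2 requires slower infusions "with vital signs monitored every 15 minutes from the start of the infusion through 60 minutes after completion of the infusion". Section 9.5.3.4 agrees: "vital signs will be monitored every 15 minutes from the start of the infusion through 60 minutes after infusion completion for any subsequent infusions". Section 9.5.3.1.1.5 restates the schedule as a recommendation: "Vital signs should be taken every 15 minutes during the infusion through 60 minutes after infusion completion".

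**The concern.** The dosing sections attach two conditions to the 30-minute watch: the patient must be past the third infusion, and must have had no infusion reaction. The checklists replace both with a calendar week. Site staff are likely to work from the checklist on the day of a visit, so a dropped condition there matters more than one dropped from a background section.

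Two kinds of patient are given the wrong line. One has had a reaction and continues dosing, which the protocol allows with optional premedication and a slower infusion. The other has had an infusion withheld for hyperglycemia under Section 9.4.6.3.2, so that the infusion number lags behind the calendar week. What is at stake is up to 30 minutes of observation at those visits.

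**Working it through.** No power, alpha or sample-size figure bears on this point. The check maps visits to infusion numbers and compares the two sets of text.

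**Step 1. Visits to infusions, none skipped** (schedules in Section 9.1)

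| Infusion | Masked period | Open-label period | Checklist AE watch |
|---|---|---|---|
| 4 | Week 9 | Week 33 | 30 min, no condition |
| 5 | Week 12 | Week 36 | 30 min, no condition |
| 6 | Week 15 | Week 39 | 30 min, no condition |
| 7 | Week 18 | Week 42 | 30 min, no condition |
| 8 | Week 21 | Week 45 | 30 min, no condition |

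That is 5 of 8 infusions for a patient dosed only in the masked period. It is 5 + 5 = 10 of 16 for a non-responder who also takes open-label TEPEZZA.

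**Step 2. Patient with a previous reaction.** If the first reaction is at infusion k of a period and no infusion is skipped, the later visits in that period with the wrong line number min(5, 8 − k):

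- k = 1, 2 or 3: 5 visits
- k = 4: 4; k = 5: 3; k = 6: 2; k = 7: 1; k = 8: 0

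The condition on previous reactions is not limited to one period. A masked-period reaction therefore adds 5 more visits if open-label treatment follows, to a maximum of 5 + 5 = 10.

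**Step 3. Vital-sign readings past the 30-minute line.** Readings fall every 15 minutes from the start of an infusion of length L. The hour after the infusion holds 60/15 = 4 readings, and its second half holds 30/15 = 2. For L = 90 they fall 15, 30, 45 and 60 minutes after the infusion. For L = 80 they fall at 10, 25, 40 and 55 minutes. Either way, 2 of the 4 required readings come after the checklist's AE watch has ended.

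**Step 4. Patient with a skipped infusion.** Section 9.4.6.3.2 lets a scheduled infusion be skipped for hyperglycemia, with dosing at the next scheduled visit, and recommends at most two skips per patient in the trial. Infusion number at a visit = scheduled number − skips earlier in that period:

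- One earlier skip: Week 9 is 4 − 1 = 3; Week 33 is 4 − 1 = 3.
- Two earlier skips: Week 12 is 5 − 2 = 3; Week 36 is 5 − 2 = 3.

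These are among the first three infusions of the period. The dosing sections require 60 minutes there even without a reaction; the checklist gives 30.

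**Step 5. What is stated and what is implied.** In step 4 a stated 60 minutes meets a stated 30. In step 2 no section gives the length of the AE watch after a previous reaction. The 30-minute allowance is withheld, and 60 minutes is inferred from the vital-sign schedule.

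**The case against.** The strongest reply is that the protocol already covers the patient who has reacted. Sections 9.4.6.3.2 and 9.5.3.4 make vital signs through 60 minutes mandatory, each affected checklist points to 9.5.3.4, and discharge follows only once all procedures are done. Leaving at 30 minutes would breach the protocol. Anaphylactic reactions, worsening rash and signs of serum sickness end dosing, so those patients should not reach later infusions. Later infusions after an event are slowed, premedication is allowed, and next-day contact follows an infusion-associated event. All of this stands and keeps the point small.

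Three stronger readings are tempting, but the documents do not support them.

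- A reader might infer that patients who have reacted are sent home unobserved at 30 minutes. The mandatory vital-sign schedule rules that out.
- A reader might infer that the checklists contradict a stated 60-minute AE watch after a reaction. No section states one; the checklists omit a condition.
- A reader might infer that the permissive vital-signs line deliberately weakens monitoring at later infusions. The same sentence appears at Day 1 and Weeks 3, 24 and 27, so it reads as standard wording. Footnote 14 of the Schedule of Assessments is firmer, "Additional vital signs will be monitored if infusion-associated AEs occur (see Section 9.5.3.4 for details", but addresses events that occur and does not by itself set a rule for earlier ones.

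The reply does not reach the patient with a skipped infusion. With no reaction, the 60-minute vital-sign rule is not triggered, and only the dosing and safety sections correct the checklist.

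**Conclusion.** The inconsistency is real and minor. The checklist line is wrong as written for a patient who has reacted and continues dosing, and for a patient whose skipped infusion places Week 9 or 33 (after two skips, Week 12 or 36) within the first three infusions of the period. For the first group the remaining risk is a site that follows the AE-watch line alone.

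The size is up to 5 visits per period, and up to 10 for a patient dosed in both. It would be wrong to conclude that a patient with no reaction is never affected, because an early skip is enough. The documents give neither a rate of infusion reactions nor a rate of skipped infusions for this population, so the number of patients cannot be estimated. The efficacy analyses are unaffected.

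This rests on two readings: that the first three infusions are counted within each period, which the 60-minute lines at Weeks 27 and 30 support, and that they are counted as infusions actually given. The visit counts in step 2 also assume that no infusion is skipped and that dosing continues to the end of the period.

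**What to change.** 1. In Sections 9.5.6.2.3, 9.5.6.2.4, 9.5.6.3.2 and 9.5.6.3.3, replace the fixed watch with: 'for 60 minutes after any of the first 3 infusions of the period or if there was any previous infusion reaction; otherwise for at least 30 minutes'.
2. In every infusion-visit checklist, including Day 1 and Weeks 3, 24 and 27, change the extra vital-signs line from 'may be performed' to 'will be performed for current or previous infusion-associated events, per Section 9.5.3.4'. Editing only the four checklists in item 1 would create a new mismatch: a patient who reacts on Day 1 already needs the fuller schedule at Week 3.
3. State the 60-minute AE watch after a previous reaction once in Section 9.4.6.3.2, to match the vital-sign schedule there.

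The cost is wording only, with no new visit or procedure. After a reaction, staff must already take vital signs for that hour. After an early skip, the dosing sections already require 60 minutes.

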#### 9.5.6.2.5 Week 24/End-of-Treatment 1/First Infusion of Open-label Treatment Period

Week 24 is the final visit of the double-masked Treatment Period. Trial drug is not administered for responders and non-responders who elect not to receive open-label TEPEZZA. For proptosis non-responders who elect to receive open-label TEPEZZA, the infusion will be performed at Week 24 (first of 8 infusions); all Week 24 procedures except AF and concomitant medication monitoring, post-infusion PK sample collection and 24-hour post-dose phone/email contact must be completed prior to TEPEZZA infusion.

- Perform efficacy assessments (proptosis, **CCI** [REDACTED] and GO-QoL questionnaire). The **CCI** will not need to be performed on the same day as other Week 24 assessments as long as it is performed within the visit window and prior to the first open-label infusion (proptosis non-responders who elect to receive open-label TEPEZZA).
- Perform CAS.
- Perform treatment response assessment, including whether the patient is a proptosis responder or non-responder, and enter data in EDC.

- Obtain blood samples for hematology and fasting chemistry (including thyroid and HbA1c) analysis.
- Collect urine sample for a pregnancy test for females of childbearing potential.
- Perform visual acuity assessment.
- Measure weight.
- Record vital signs (prior to and at the end of the infusion for non-responders who elect to receive open-label TEPEZZA). Additional vital sign monitoring may be performed in the event of infusion-associated AEs (see Section 9.5.3.4 for details).
- Collect blood samples for immunogenicity and **CCI** (NOTE: Collection should be prior to dose for non-responders who elect to receive open-label TEPEZZA.) Collect a single blood sample for PK analyses (proptosis responders and proptosis non-responders who elect not to receive open-label TEPEZZA). NOTE: **CCI**

**CCI**

- Inquire about AEs and concomitant medication use.
- Take photograph of the patient's eyes for those patients who have consented.
- Obtain calculated dose, vial assignment and volume of TFPZ7A to be administered from the EDC system for non-responders who elect to receive open-label TEPEZZA only.
- Collect blood samples for PK analyses prior to and at the end of the infusion (non-responders who elect to receive open-label TEPEZZA only).
- Administer TEPEZZA and record date, volume and start/stop times of the infusion (non-responders who elect to receive open-label TEPEZZA only).
- Enter remaining visit data in the EDC system.

Patients will be discharged from the site after all procedures have been completed. Patients who are proptosis responders, as well as non-responders who elect not to receive open-label TEPEZZA, will enter the Follow-up Period and will be contacted via phone or email in 30 days. Patients in the open-label Treatment Period will be instructed to return for a clinic visit in 3 weeks and will be contacted the following day to perform a safety check following the first open-label infusion.

### 9.5.6.3 Open-label Treatment Period Visits After Week 24 – Proptosis Non-responders Who Choose to Receive Open-label TEPEZZA

Proptosis non-responders who elect to receive open-label TEPEZZA during the open-label Treatment Period will receive additional infusions at Weeks 27, 30, 33, 36, 39, 42 and 45.

#### 9.5.6.3.1 Week 27

- Collect predose urine sample for a pregnancy test for females of childbearing potential; the pregnancy test must be negative for the patient to receive TEPEZZA.
- Perform efficacy assessments (proptosis, **CCI**).
- Inquire about AEs and concomitant medication use.
- Collect blood samples for PK analyses prior to and at the end of the infusion.
- Collect predose blood sample for immunogenicity testing.
- Record vital signs prior to and at the end of the infusion. Additional vital sign monitoring may be performed in the event of infusion-associated AEs (see [Section 9.5.3.4](#) for details).
- Obtain calculated dose, vial assignment and volume of TEPEZZA to be administered from the EDC system.
- Administer TEPEZZA and record date, volume and start/stop times of the infusion. Monitor the patient for any AEs during the infusion and for 60 minutes after the completion of the infusion.
- Enter visit data in the EDC system.

Patients will be discharged from the site after all procedures have been completed, instructed to return for a clinic visit in 3 weeks and contacted the following day to perform a safety check following the second open-label infusion.

#### 9.5.6.3.2 Weeks 30, 36 and 42

- Collect predose urine sample for a pregnancy test for females of childbearing potential; the pregnancy test must be negative for the patient to receive TEPEZZA.
- Obtain predose blood samples for hematology and fasting chemistry (including thyroid and HbA1c at Week 36 only).
- Inquire about AEs and concomitant medication use.

- Perform predose visual acuity assessment.
- Perform predose efficacy assessments (proptosis, **CCI** [redacted] as well as GO-QoL questionnaire [Weeks 30 and 36 only]).
- Perform predose CAS at Week 36 only.
- Collect predose blood samples for PK analysis and immunogenicity testing at Week 36 only.
- Record vital signs prior to the infusion. Additional vital sign monitoring may be performed in the event of infusion-associated AEs (see [Section 9.5.3.4](#) for details).
- Obtain calculated dose, vial assignment and volume of TEPEZZA to be administered from the EDC system.
- Administer TEPEZZA and record date, volume and start/stop times of the infusion. Monitor the patient for any AEs during the infusion and for 60 minutes (Week 30) or 30 minutes (Week 36 and Week 42) after the completion of the infusion.
- Enter visit data in the EDC system.

Patients will be discharged from the site after all procedures have been completed and instructed to return for a clinic visit in 3 weeks.

#### 9.5.6.3.3 Weeks 33, 39 and 45

- Collect predose urine sample for a pregnancy test for females of childbearing potential; the pregnancy test must be negative for the patient to receive TEPEZZA.
- Inquire about AEs and concomitant medication use.
- Measure predose weight (Week 33 only).
- Record vital signs prior to the infusion. Additional vital sign monitoring may be performed in the event of infusion-associated AEs (see [Section 9.5.3.4](#) for details).
- Obtain calculated dose, vial assignment and volume of TEPEZZA to be administered from the EDC system.
- Administer TEPEZZA and record date, volume and start/stop times of the infusion. Monitor the patient for any AEs during the infusion and for 30 minutes after the completion of the infusion.

- Enter visit data in the EDC system.

Patients will be discharged from the site after all procedures have been completed and instructed to return for a clinic visit in 3 weeks.

